
Furthermore, our expectation is that this difference will be most apparent at 48 hrs. as discussed above with a reduction in narcotic requirements greater than 40% in the continuous catheter TAP group vs. standard single shot Bupivacaine TAP (4.1 mg +/- 3 mg vs. 2.4 mg +/- 1.3 mg Dilaudid). This is based on the assumption that the effects of the local anesthetic control TAP (single shot Bupivacaine) may last up to 24 hrs. At 72 hrs, prior studies, although limited, have not shown a significant difference between TAP block and placebo groups.

c Study Objectives

Primary Aim

The primary aim is to evaluate for any significant difference total post-operative narcotic requirements (Dilaudid) required over 48 hrs. in the continuous catheter TAP block arm vs. the single shot Bupivacaine TAP arm and again the slow release Liposomal Exparel® TAP arm vs. the single shot Bupivacaine TAP arm.

Secondary Aim

The secondary aim will be to evaluate for any significant difference in narcotic requirements at other endpoints such as 24 hrs and at 72 hrs. As discussed before, current studies do not show a significant difference when extrapolated out at those end points, albeit there is very little data at 72 hrs. Other quality indicators of recovery in the three arms such as Visual Analog Scores (VAS) are expected again to be most significantly different at 48 hrs. Other quality measures that will be recorded include incidence and severity of post-operative nausea and vomiting (PONV), time to ambulation, and patient satisfaction with post-operative pain control.

Rationale for the Selection of Outcome Measures

Outcome measurements are based on the assumption that narcotic requirements (i.e. intravenous Dilaudid Patient-Controlled Analgesia [PCA] use) are inversely related to patient satisfaction in regards to their post-operative pain. Additional factors such as VAS, ambulation, performance of daily activities, and anti-emetic pharmaceutical requirements have been chosen as quality indicators in regards to post-operative pain control and dependence on narcotics.

D Investigational Agent

This investigation will use three FDA-approved techniques:

- Bilateral Continuous TAP block via Catheter (One-time bolus of Bupivacaine 0.25% x 20ml per side followed by continuous infusion of Ropivacaine 0.2% 7 ml/hr. per side x 48 hrs.);
- Single Injection TAP block with Exparel® (One-time bolus of Bupivacaine 0.25% x 20 ml followed by Exparel 133 mg per side); and

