- Single Injection TAP block with Bupivacaine 0.25% (25 ml-30 ml volume one-time bolus per side).

E Study Design

Overview or Design Summary

It is the purpose of this study to evaluate the efficacy of continuous TAP block via catheter versus single shot Bupivacaine TAP block and also to evaluate the efficacy of slow release Exparel® versus single shot Bupivacaine. The study shall consist of three (3) arms of which patients will be randomly assigned: Bilateral Continuous TAP block via Catheter (One time bolus of Bupivacaine 0.25% x 20 ml per side followed by continuous infusion of Ropivacaine 0.2% 7 ml/hr. per side x 48 hrs); Single Injection TAP block with Exparel® (One time bolus of Bupivacaine 0.25% x 20 ml followed by Exparel 133 mg per side); and Single Injection TAP block with Bupivacaine 0.25% (25-30 ml volume one time bolus per side). Several parameters will be measured with the primary goal being to determine the effectiveness and duration of post-operative pain relief of the newer techniques of extending TAP block duration with the current, commonly used standard single shot Bupivacaine technique. Because a goal of this study is to determine which technique of TAP block is most effective for post-operative pain control, the three (3) arms of this study will be performed in a manner that is most consistent and common with current anesthesia practice. Because TAP block is typically most effective for lower and mid-abdominal incisional pain relief, the nature and height of the incision with regard to the umbilicus will also be recorded.

Parameters Measured:

- 1) Total Post-operative Narcotic Requirements over at 24, 48 and 72hrs.
- 2) Days of IV PCA use: Time to 1st dose, total IV PCA requirements, POD# 0, 1, 2, & 3, additional narcotic use and additional adjuvants
- 3) PACU narcotic requirements
- 4) Pain Score:0-10 on post-operative day (POD)# 0, POD #1, POD #2, POD #3 (am, pm, Max Pain score per day, Pain score at rest, and Pain score with activity)
- 5) Day to Ambulation: O=out of bed assisted/unassisted, W= walk with/without assistance

- 6) Day of Foley removal
- 7) Day of first Bowel Movement
- 8) Anti-emetic Drug (Zofran) requirements.
- 9) Surgical Incisional height in relation to umbilicus or Type of Surgery (recorded by anesthesiologist)
- 10) Anesthesia provider placing TAP block
- 11) Patient weight/BMI
- 12) Day of discharge

Subject Selection and Withdrawal

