Patient characteristics and outcomes data will be summarized by cross-tabulation (categorical variables), quartiles (median, ordinal variables), and mean and standard deviation (continuous variables). Comparisons between groups will use Chi-square test or Fisher's exact test as appropriate for categorical variables and t-test or Wilcoxon rank-sum test as appropriate for continuous variables.

Analyses of primary outcome will examine differences in mean opioid consumption between the single shot TAP group and the Exparel TAP group. Analyses of secondary outcomes will examine differences in mean opioid consumption between the single shot TAP group and continuous TAP group. Treatment groups will be compared using a

student's t-test if data are normal distributed or Wilcoxon rank-sum test if not normal distributed.

The differences in mean opioid consumption across three groups (single shot TAP, continuous TAP, and Exparel TAP) will be examined with a test of means between groups using one-way analysis of variance (ANOVA). A comparison between continuous TAP and Exparel TAP will be performed. A t-test will be used if the observations in each trial arm are normally distributed; if non-normally distributed, then rank-based methods such as Wilcoxon rank-sum test will be employed.

All tests will be two-sided.

The overall incidence of serious adverse events and adverse events and number and proportion of patients reporting such events will be summarized by treatment group. Adverse events will be tabulated and summarized by the number and percentage of subjects who experienced the event.

Missing Outcome Data

Analysis will be conducted as described in prior section. Missing data will not be included in the analysis; however, may lead to an increase in patients recruited into one or more study arms.

Unblinding Procedures

This study is not blinded because it will be obvious to all care givers whether or not the patient received a continuous block with catheters or not.

H Data Handling and Record Keeping

Confidentiality and Security

Data will be collected on the data collection forms located in Attachment L9 and entered into the Oncore ERM study management system.

Data collection forms will be stored at each respective study site within a locked cabinet in a locked research office.

The Oncore ERM study management system is a secure web-based management system that is password-protected. Access to data is role-specific.

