Schedule of Measurements Template (add additional information as needed)

Anesthesiologist performing TAP BLOCK	Surgeon
Date of Surgery	Hospital Discharge Date
Procedure  Ventral hernia  Expl. Lap  Colon  Small Bowel  Anterior Resection  APR  Lower Anterior Resection  Prostate  TAH  HIPEC  Cyto-reductive Surgery  Ileostomy reversal  Robotic Assisted +/- Hand Assisted  Robotic (no incision)  L/S Assisted +/- Hand Assisted  L/S (no incision)  Other _____	 Continuous TAP with Ropiv 0.2%  Single Shot TAP  Exparel  0.25% Bupivacaine  Pre-incision  Post-incision Other: _____

PATIENT INFORMATION

Initials	Outpatient / SDA  Patient taking narcotics at home prior to surgery?  Yes  No	Inpatient (prior to Surgery)  PCA  IV narcotics  (skip if PCA) P.O. Narcotics  (skip if PCA)	
Age	Gender  M  F	Race  Cauc  Black (Non Hisp)  Hisp  Asian  Other	ASA
BMI	Smoking  Yes  No	Diabetes  Yes  No	
Incisional Dermatone Level Range: (Umb=T10)	Surgery Duration (minutes)	PACU Time until nurse gives report	

Outcomes	PACU	POD 0	POD 1	POD 2	POD 3
PCA		 Y  N	 Y  N	 Y  N	 Y  N
NARCOTICS					
MSO4 (mg) total requirements					
Dilaudid (mg) total requirements					
Fentanyl (mg) total requirements					
Anti-emetic Given (+/-)					
EVENTS					
Bowel Movement (+/-) (record 1 st day only)					

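### Anti-emetic requirements are a listed outcome, but the supplied form records only given or not given per period, so the amount used cannot be recovered

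*Combined protocol and SAP*

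**What the plan says.** Section C (Rationale for the Selection of Outcome Measures) states that "anti-emetic pharmaceutical requirements have been chosen as quality indicators" for pain control and dependence on narcotics. Section E, Parameters Measured, item 8, lists "Anti-emetic Drug (Zofran) requirements". The Secondary Aim in section C also promises both the incidence and the severity of postoperative nausea and vomiting.

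The Outcomes table of the form in section L has five columns: PACU and postoperative days 0, 1, 2 and 3. Its anti-emetic row reads "Anti-emetic Given" and takes a plus or minus in each column. The opioid rows in the same table take amounts, for example "Dilaudid (mg) total requirements". The form has no field for anti-emetic dose or number of doses, and none for severity of nausea or vomiting. Its heading describes it as a template that may be extended.

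The Statistical Analysis Plan in section G sets tests by type of variable: "Chi-square test or Fisher's exact test as appropriate for categorical variables", and t-test or Wilcoxon rank-sum for continuous ones. It does not mention anti-emetic use and does not say how the five plus/minus entries become one value per patient. The sample size section claims power for opioid consumption only.

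**The concern.** A requirement for a drug is naturally read as an amount, and the form itself uses the word that way for opioids. For anti-emetics the amount is discarded when the data are recorded. A patient with one dose on a given day and a patient with four get the same entry, and no later analysis can separate them.

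The item bears on the trial's rationale. The background section argues that TAP block may reduce narcotic side effects such as nausea and vomiting, and this row is the only item on the supplied form related to that claim. If the entries were reduced to ever/never use and most patients received at least one dose, the measure would sit near its ceiling. A real fall in anti-emetic use could then be reported as no difference in a quantity that was never measured.

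**Working it through.** **1. The plan's own figure.** The only power statement concerns opioid consumption: 4.1 against 2.4 mg, SD 3, two-sided 0.05, 80% power. n = 2 × (1.96 + 0.8416)² × (3/1.7)² = 48.9, so 49 per arm, as stated. Recruiting 53 per arm with 10% dropout leaves 53 × 0.9 = 47.7, about 48 evaluable per arm. No rate, dose distribution, effect or power is given for anti-emetic use, so everything below rests on assumptions.

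**2. Assumptions.** 48 per arm. Doses per patient are Poisson with gamma between-patient variation of shape 1. The treated mean is the control mean × 2.4/4.1 = 0.585, borrowed from the opioid assumption. Doses are spread over the five form periods with weights 0.15, 0.25, 0.30, 0.20 and 0.10. The control mean is varied because the documents do not give it.

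**3. Ever/never, by formula.** Under this model P(any dose) = m/(1 + m) for mean m. Power is about Φ(|p₁ − p₂|/SE − 1.96), with SE = √(2p̄(1 − p̄)/48).
- Control mean 1: p₁ = 0.500; treated mean 0.585, p₂ = 0.369; p̄ = 0.435; SE = 0.101; z = 1.29; power = Φ(−0.67) ≈ 25%.
- Control mean 4: p₁ = 0.800; treated mean 2.34, p₂ = 0.701; p̄ = 0.750; SE = 0.088; z = 1.12; power = Φ(−0.84) ≈ 20%.

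**4. Simulation of three summaries** (1,500 replicates per setting):

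| Control mean doses | Ever/never, chi-square | Positive periods (0-5), Wilcoxon | Total doses, Wilcoxon |
|---|---|---|---|
| 1 | 26% | 32% | 33% |
| 2 | 25% | 40% | 42% |
| 4 | 22% | 46% | 50% |
| 6 | 18% | 46% | 52% |

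A rerun gave 20% for ever/never at a mean of 4, in line with the formula, hence 20-22%.

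**5. Where the loss disappears.** In the same model at lower control means, the gain from total doses over ever/never is about zero at 0.3 doses and about 1 to 4 points at 0.5.

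**6. Other assumed effects (49 per arm).**
- Treatment halves the chance of any drug and leaves the amount among users unchanged: power for amount against yes/no is 42% and 43% at 30% control use, 70% and 73% at 50%, and 90% and 95% at 70%. Yes/no is as good or better.
- Treatment changes only the amount among users: power on the amount is 9% to 58%, and yes/no stays at about 5-6%, close to the significance level.

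**7. What the existing form can still give.** Between the last two columns in step 4, the count of positive periods falls short of total doses by 1 point (33 − 32), 2 (42 − 40), 4 (50 − 46) and 6 (52 − 46). Most of the loss from ever/never is therefore recoverable without changing the form, although the amount itself is not.

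**The case against.** Two stronger readings are tempting. The documents support neither.

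The first is that the plan prescribes a chi-square or Fisher test of ever/never use. It does not. The rule is general, anti-emetic use is not named, and nothing says that the five entries are collapsed. The plan also provides ordinal summaries and a Wilcoxon test, so a 0-5 count of positive periods would fit its text.

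The second is that a clear loss of power is certain. With no anti-emetic rate in the documents, low use cannot be excluded, and there the loss is negligible. If treatment acts only on whether any drug is given, a binary measure does at least as well.

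Three further points have weight. A plus/minus entry does serve the incidence of side effects, which the plan also wants, though not severity. Better recording does not make this a well-powered comparison: total doses reach only 33% to 52% in the table. And section H places the data collection forms in Attachment L9, which cannot be identified in the supplied text, so only the form in section L can be checked.

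These points limit the size of the concern. They do not remove the mismatch: the outcome is named as a requirement, and the form that can be checked has no place for an amount.

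**Conclusion.** The mismatch between outcome and form is real and does not depend on any assumption. If the form is used as written, anti-emetic requirements cannot be measured; only use or non-use in each of five periods can.

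The effect on power is conditional. If the entries were reduced to ever/never and use were common, the assumed dose-count model gives a loss of about 7 points at a control mean of 1 dose (33 − 26) and 28 to 30 points at a mean of 4 (50 − 22 and 50 − 20). At means of 0.5 or below, or if treatment changes only whether any drug is given, the loss is small or absent. These figures rest on the assumed dose distribution, the borrowed opioid ratio and 48 evaluable patients per arm.

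This is a minor point about an unpowered secondary quality indicator. The primary outcome and its sample size are unaffected.

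**What to change.** Change the existing anti-emetic row to the number of doses, or total mg of Zofran, in each period, as the form already does for opioids. Add one sentence to section G: the per-patient total is compared between arms by the Wilcoxon rank-sum test already in the plan, and any/none is reported as a descriptive incidence.

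If the form cannot change, name the outcome as the number of periods with anti-emetic use (0 to 5), prespecify that summary, and compare it by Wilcoxon. Do not describe it as a requirement or an amount.

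The cost is slightly more chart abstraction: a number in place of a plus or minus. No extra patients or study procedures are needed, and the form's heading already allows additions. If the Attachment L9 form already records doses, only the analysis sentence and the alignment of the section L form remain.
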